## **1.2. Filgotinib (GS-6034)**

### **1.2.1. General Information**

Janus kinases (JAKs) are intracellular cytoplasmic tyrosine kinases (TYKs) that transduce cytokine signaling from membrane receptors through signal transducer and activator of transcription (STAT) to the nucleus of cells. JAK inhibitors block the signaling of various cytokines, growth factors, and hormones, including the proinflammatory cytokine interleukin (IL)-6. Four different types of JAKs are known, JAK1, JAK2, JAK3, and TYK2 which interact with different sets of membrane receptors. Inhibition of JAKs is a promising therapeutic option for a range of inflammatory conditions including rheumatoid arthritis (RA) and CD.

Filgotinib (GS-6034, formerly known as GLPG0634) is a potent and selective inhibitor of JAK1. Filgotinib is approved in the European Union (EU), Japan, and Great Britain for treatment of moderate to severe active RA in adult patients. It is also approved for the treatment of moderately to severely active ulcerative colitis (UC) in adults in the EU, Japan and Great Britain. The compound has shown good preliminary efficacy in CD patients in Phase 2 studies.

In humans, filgotinib is metabolized to form one major active metabolite, GS-829845. Though the potency of this metabolite is lower than the parent molecule, the overall exposure and peak plasma concentration in humans is higher than seen in all tested animal species. As a consequence, dedicated pharmacology and toxicology studies have been performed with GS-829845. Results from pharmacodynamics (PD) testing in healthy volunteers suggest that the clinical activity of filgotinib could result from the combination of the parent molecule and the metabolite.

For further information on filgotinib, refer to the current Investigator's Brochure (IB).

### **1.2.2. Preclinical Pharmacology and Toxicology**

Filgotinib and its metabolite, GS-829845 have been extensively characterized in nonclinical studies. This program includes cellular assays demonstrating potency and selectivity of the compound against JAK1; efficacy studies in rats and mice; repeat-dose toxicity studies (up to 26 weeks in the rat and 39 weeks in the dog), in vitro and in vivo safety pharmacology and genetic toxicology studies, and reproductive toxicology studies in rats and rabbits.

Additional toxicology studies conducted include phototoxicity studies and dose-range finding studies in support of a definitive juvenile toxicity study. A definitive juvenile toxicology study in rats is ongoing.

### 1.2.2.1. Nonclinical Pharmacology

In cellular assays, filgotinib inhibits JAK1 signaling with the concentration of an inhibitor that is required for 50% inhibition ( $IC_{50}$ ) values of  $\geq 179$  nM, and demonstrates 30-fold selectivity over JAK2 in a human whole blood assay. Filgotinib has been profiled against 451 kinases and it is highly selective for JAK1; only 2.5% of kinases were inhibited  $\geq 50\%$  at 50-fold higher concentration than  $IC_{50}$  for JAK1. Broad receptor profiling ( $\sim 70$  receptors, ion channels, transporters and enzymes) did not reveal any off-target liabilities of the compound. Filgotinib demonstrated high potency in the rat collagen-induced arthritis (CIA) model as well as in the mouse dextran sulfate sodium (DSS)-induced colitis model, the latter of which is detailed below. The major human metabolite of filgotinib GS-829845 exhibits a similar JAK1 selectivity profile but is approximately 10-fold less potent as compared to parent filgotinib in vitro.

The efficacy of filgotinib was evaluated in a prophylactic setting of the chronic mouse Dextran DSS model in two separate studies. Both studies evaluated oral dose levels of 10 and 30 mg/kg once daily. In addition to assessments of clinical score (disease activity index [DAI] and colon lesion score), serum markers of inflammation, immunohistochemical analysis, and expression of various chemokines and cytokines known to be altered in CD and UC patients were also evaluated in the distal colon of these mice.

In both studies, the DAI score, which takes into account body weight loss, rectal bleeding, and stool consistency, was reduced by filgotinib in a dose-dependent manner, demonstrating that filgotinib protected mice against colitis induced by DSS. Histology of the colon revealed a filgotinib-mediated dose-related reduction in colon lesion score, correlating with reductions in DAI score.

Additional end points evaluated across the DSS colitis model studies confirmed the suppression of various inflammatory markers including serum levels of C-reactive protein (CRP) and myeloperoxidase (MPO) and expression of IL-6 and TNF $\alpha$  (by reverse transcription polymerase chain reaction [RT-PCR]) by filgotinib. Immunohistochemical analysis of the colon confirmed inhibition of the JAK-STAT pathway by filgotinib as evidenced by a reduction of DSS-induced STAT3 phosphorylation.

### 1.2.2.2. Safety Pharmacology

Filgotinib and GS-829845 had no relevant effects on cardiovascular parameters (human ether-a-go-go [hERG] and dog telemetry studies), apart from a slight non-adverse increase in heart rate and arterial pressure with GS-829845 at exposures 8-fold that of the peak serum concentration ( $C_{max}$ ) in subjects with CD treated with 200 mg once daily filgotinib. There were no relevant effects on electrocardiogram (ECG) and QT. Filgotinib and GS-829845 had no effects on the respiratory system and central nervous system (CNS).

### 1.2.2.3. Key Nonclinical Distribution, Metabolism, and Excretion Data

Filgotinib demonstrates good oral bioavailability in mice, rats, dogs, and mini-pigs but less in monkeys. Plasma protein binding is low ( $< 70\%$ ) in all species, including humans.

The pharmacokinetics (PK) of filgotinib is generally dose proportional without gender differences. No accumulation occurs with repeated dosing. The mean terminal half-life after oral administration is 4 hours and 5 hours in rats and dogs, respectively.

In the rat, filgotinib showed a rapid and even distribution throughout the body. High concentrations were observed only in the gastrointestinal (GI) tract and urinary bladder. Filgotinib does not penetrate into CNS tissues. The distribution of filgotinib indicates some affinity for melanin-containing tissues.

Excretion is nearly complete within 24 hours (rat) and 48 hours (dog) post-dosing. In the rat, fecal and urinary excretion accounted for 40% and 53% of the administered dose, respectively, with a bile secretion of about 15%. In the dog, fecal excretion was the primary route of excretion, accounting for 59% of the administered dose, with urinary excretion accounting for 25%.

In vitro metabolism studies in all species revealed one major metabolite (GS-829845). The formation of GS-829845 is mediated by carboxylesterases (CES) and is not dependent on cytochrome P450 (CYP).

In vitro experiments have shown that drug-drug interactions with filgotinib and GS-829845 are unlikely. There is no inhibition or induction of CYPs or uridine 5'-diphosphate - glucuronosyltransferase (UGTs), and no relevant inhibition of key drug transporters, including organic anion transporters (OATs), by filgotinib or GS-829845. OCT2 was inhibited by both filgotinib ( $IC_{50}$ : 8.7  $\mu$ M) and GS-829845 ( $IC_{50}$ : 67  $\mu$ M). The clinical relevance of the  $IC_{50}$  values for inhibition of OCT2 will be further evaluated. MATE1 was also weakly inhibited by filgotinib ( $IC_{50}$ : 94  $\mu$ M) and GS-829845 ( $IC_{50}$ : >100  $\mu$ M). Filgotinib was found to be a substrate of P-glycoprotein (P-gp).

#### **1.2.2.4. Nonclinical Toxicology**

In repeat oral dose toxicity studies in both rats and dogs, the primary target tissues identified for filgotinib were the lymphoid tissues which are expected based on the pharmacology of JAK inhibition. Additional filgotinib-related findings were observed in the male reproductive organs of both species, and in the incisor teeth of rats only. Effects on the lymphoid system were fully reversible. Testicular toxicity demonstrated partial reversibility; however, sperm counts remained low. When using the mean exposure (AUC) at the NOAELs for the most sensitive species (the dog), the exposure margins compared to a 200 mg once daily dose of filgotinib in CD subjects are 2.5, 1.9, and 3.6-fold for the 26-week and 39-week chronic toxicity studies and the 39-week targeted exposure toxicity study, respectively.

GS-829845-related findings in the repeat-dose toxicity studies were generally similar to those of the parent filgotinib; however, no testicular toxicity was noted following administration of GS-829845.

Filgotinib and GS-829845 were non-genotoxic when evaluated in the bacterial mutagenicity assay, the in vitro mouse lymphoma mutagenicity assay, and the rat bone marrow micronucleus assay.

In embryofetal development studies, filgotinib and GS-829845 caused embryoletality and teratogenicity in rats and rabbits. Teratogenicity was observed at exposures slightly higher or similar to the human exposure at 200 mg once daily of filgotinib in subjects with CD. Administration of filgotinib did not affect female fertility but impaired fertility was observed in male rats at exposures approximately 12-fold the human exposure at 200 mg of filgotinib in subjects with CD. GS-829845 did not have any effects on fertility parameters in either male or female rats.

In an in vitro phototoxicity study in 3T3 cells, the metabolite GS-829845 was positive for phototoxic potential and results with filgotinib were equivocal. A follow-up in vivo rat phototoxicity assay revealed a lack of phototoxic potential for both compounds.

### **1.2.3. Clinical Trials of Filgotinib**

An overview of exposure and clinical studies conducted with filgotinib is available in the IB.

#### **1.2.3.1. Phase 2 Study in Crohn's Disease (GLPG0634-CL-211, FITZROY)**

A Phase 2, randomized, double-blind, placebo-controlled, multicenter study with filgotinib was performed in subjects with active CD with evidence of mucosal ulceration {[Vermeire 2017](#)}. In Part 1, a total of 174 subjects were randomized (3:1) to receive either filgotinib 200 mg once daily or placebo for 10 weeks. Based on their clinical response in Part 1, subjects in Part 2 either continued their current treatment or were reassigned to a different treatment for an additional 10 weeks.

The efficacy of filgotinib was assessed by evaluating clinical remission (defined as CDAI score < 150), clinical response (defined as a decrease in CDAI of at least 100 points from baseline), and endoscopic response (defined as a decrease of at least 50% from baseline in the SES-CD score).

The primary end point of the study was met: at Week 10, 60 of 128 subjects (46.9%) who received filgotinib achieved clinical remission versus 10 of 44 subjects (22.7%) who received placebo, a difference of 24.1% (P-value = 0.0077). In addition, filgotinib treatment was associated with increases in the proportion of subjects with clinical and endoscopic response compared with placebo.

Overall, the safety profile of filgotinib in CD subjects was consistent with prior studies.

For additional details about the efficacy and safety of filgotinib in CD, reference is made to the IB.

### **1.3. Rationale for This Study**

A need for safer, better tolerated, durable efficacious therapies for patients with CD exists. Despite significant uptake in the use of anti-TNF agents, tolerability of anti-TNFs due to allergic and autoimmune reactions, lack of durable response, and significant increased risk of infection remain problematic. Filgotinib is a once daily, oral therapy that may prove efficacious without the risk of allergic and autoimmune phenomena observed with anti-TNF agents.

This is a long-term extension study (GS-US-419-3896; Galapagos Study ID GLPG0634-CL-310 [DIVERSITY LTE]) to provide treatment with filgotinib for subjects with moderately to severely active CD (who have completed or met protocol specified efficacy discontinuation criteria in a prior filgotinib treatment study for CD) until filgotinib becomes commercially available in the country or until the end of study (31 January 2025), whichever comes first..

The purpose of this study is to observe the safety of long-term therapy and to ensure continued access to study drug for subjects who responded in the parent protocol of filgotinib. In addition, the study provides an open-label alternative at the highest possible dose (excluding males who are not dual-biologic refractory in the US and Korea, refer to Section 3.3 for further information) for subjects who had disease worsening or lack of response in the parent study.

### 1.3.1. Rationale for Dose

In Phase 2 trials in RA, pooled data with an exposure – response analysis demonstrated a dose-dependent increase in efficacy up to 200 mg total daily dose. In the Phase 2 study of CD, subjects treated in the 200 mg arm showed favorable response and remission rates (47% remission over 23% placebo and 59% response over 41% placebo). Remission rates at Week 20 for subjects who failed placebo for the first 10 weeks and commenced 100 mg from Weeks 10 to 20 was slightly lower (32%) though response rate was comparable (59%), indicating some level of efficacy at the 100 mg dose. These results are consistent with the relationship observed between filgotinib exposures and inhibition of pSTAT1 activation (ex-vivo) following single and multiple filgotinib doses, where maximal inhibition of pSTAT1 activation (~78%) was achieved at or above 200 mg total daily dose and intermediate inhibition (~47%) at 100 mg {[Namour 2015](#)}. pSTAT1 data, in conjunction with considerations around the margin for nonclinical testicular findings, suggests assessing doses above 200 mg is not indicated. The presence of response in CD subjects in the exploratory 10 to 20 week arm of Study GLPG0634-CL-211, and study of multiple doses (ie, 100 mg and 200 mg once daily) in the present study will enable establishment of an appropriate nominal dose and determine the dose with the most favorable risk/benefit profile for CD subjects. The present study will ensure continued access to blinded dosing for specific subjects (those who complete a respective parent protocol through the end of that study). After the corresponding parent study (GS-US-419-4015, GS-US-419-4016, or GS-US-419-3895 [Galapagos Study ID: GLPG0634-CL-309]) is unblinded, subjects enrolled in the present study may be unblinded. Subjects who enroll from a parent study and receive blinded treatment in the DIVERSITY LTE study will have their DIVERSITY LTE treatment assignment unblinded when the parent study is unblinded. Subjects will continue on the same dose of open-label filgotinib as they had been receiving in blinded treatment. Subjects on placebo treatment will discontinue study drug and study participation. In addition, the present study allows open-label access at the highest possible dose for subjects who were non-responders or experienced disease worsening on blinded dosing in a parent study. At no time will males in the US and Korea who are not dual biologic refractory receive 200 mg.

Subjects enrolled from other filgotinib treatment studies for CD will receive open-label 200 mg filgotinib daily. Reference is made to Section 3.3 for details about dosing regimen and definition of being dual biologic refractory.

#### 1.4. Risk/Benefit Assessment for the Study

Crohn's disease is a progressive and potentially life-threatening disease with few treatment options, many of which result in primary or secondary nonresponse. Inflammatory bowel disease may lead to increased risk of gastrointestinal malignancies, impairment in quality of life, and ultimate need for life-altering surgery. Current treatment options are limited in ability to establish mucosal healing and clinical remission and have significant safety and efficacy limitations; for example, biologics have significant immunogenic risks and steroids are associated with increased morbidity and mortality. Remission rates are generally low when compared to placebo rates across most therapies for IBD. There remains substantial unmet need in IBD, particularly in moderate to severe disease. The lifelong nature of IBD increases the probability that subjects have cycled through various therapies, leaving few approved options.

Nonclinical studies in rats and dogs identified lymphoid tissues and testes as target organs for filgotinib in long-term repeat-dose toxicity studies. Although decreased lymphocyte numbers observed in nonclinical studies have not been seen in clinical studies, hematological assessment will be performed throughout the present study to ensure this potential risk is appropriately monitored. In both rats and dogs, microscopic findings in the testes included germ cell depletion and degeneration, with reduced sperm content and increased cell debris in the epididymis and reduction in fertility in male rats. The dog was determined to be the most sensitive species. When using the (AUC at the NOAELs for dogs in the 26-week and 39-week chronic toxicity studies, and the 39 week targeted exposure toxicity study, the exposure margins compared with the highest proposed clinical dose of 200 mg once daily are 2.5, 1.9 and 3.6-fold respectively, in subjects with CD. A male safety study is planned to examine the potential effect of filgotinib on sperm/ejaculate parameters. Pending those results, the use of 200 mg in males in the US and Korea with CD or UC will be limited to subjects who have failed at least two biologic therapies (any TNF $\alpha$  antagonist and vedolizumab). Refer to the IB for further information about nonclinical and clinical testicular findings.

Filgotinib has shown an increase of embryofetal malformations in rats and rabbits at exposures similar to, or slightly higher than, exposures associated with a 200 mg once daily dose in CD subjects, the use of highly effective contraception in the subject population is expected to mitigate this risk.

JAK inhibition is expected to increase the risk of infection based on mechanism of action. Across the global studies in filgotinib, in general, active treated arms have increased incidences of infection versus placebo. In the present protocol, treatment interruption and discontinuation considerations surrounding infections are incorporated and sites and investigators will be trained regarding such circumstances. All subjects will be screened for tuberculosis (TB) and subjects with clinically significant active infections will be excluded. Malignancy has been reported in subjects on filgotinib; in the present trial, subjects will be required to have up to date colorectal cancer screening and surveillance and subjects with recent malignancies will be excluded as outlined in the inclusion criteria in the parent study. For further details about infections and malignancies, please refer to the IB.

The potential benefits of JAK inhibition include improvement in clinical symptoms and mucosal and [REDACTED]. JAK inhibition may be efficacious in the treatment of IBD based on

results from FITZROY. In FITZROY, an increase in mean hemoglobin concentration was observed, without difference between filgotinib and placebo. No clinically significant changes from baseline in mean neutrophil counts or liver function tests were observed at 10 weeks. Filgotinib treated subjects showed an increase in HDL and no significant change in LDL. Lipid and hemoglobin effects represent potential benefits in this population.

Taking all of these considerations into account with respect to the filgotinib program, the early signals for efficacy demonstrated in the CD clinical trials, as well as the beneficial findings in nonclinical models of disease and the overall safety, tolerability, and PK characteristics of filgotinib that have been elucidated to date, there is a favorable benefit-risk profile for this agent in continued development as a treatment for CD. The overall risk/benefit balance of this study is considered favorable.

For additional information about the risks of filgotinib, reference is made to the filgotinib IB.

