### **Exclusion Criteria**

Subjects who meet *any* of the following exclusion criteria are not to be enrolled in the study.

- 1) Subjects who are discontinued from a parent study for reasons *other* than disease worsening or lack of response or remission; eg, subjects who discontinue for safety or tolerability issues are not eligible for this study
- 2) Known hypersensitivity to the study drug
- 3) Any chronic medical condition (including, but not limited to, cardiac or pulmonary disease, alcohol or drug abuse) that, in the opinion of the Investigator or Sponsor, would make the subject unsuitable for the study or would prevent compliance with the study protocol
- 4) Criterion modified per amendment 9
  - 4.1) Females who may wish to become pregnant and/or plan to undergo egg donation or egg harvesting for the purpose of current or future fertilization during the course of the study and for at least 30 days after the last dose of study drug
- 5) Criterion deleted per amendment 9
- 6) Criterion modified per amendment 9
  - 6.1) Females of reproductive potential who are unwilling to abide by protocol-specified contraceptive methods as defined in [Appendix 6](#)
- 7) Use of prohibited concomitant medications as outlined in [Section 5.4.2](#)

Study Procedures/  
Frequency:

Study visits with safety procedures will occur at Week 2, Week 4, Week 12, and then every 12 weeks thereafter, until the End of Treatment (EoT) visit. The EoT visit will be scheduled when filgotinib becomes commercially available in the country or prior to the end of study on 31 January 2025, whichever comes first.

Day 1 assessments will include medical history, symptom directed physical examination (PE) including body weight and height, vital signs, safety laboratory assessments, urine pregnancy test (for females of childbearing potential), PRO2 and CDAI, adverse events (AEs) and concomitant medication assessments.

PRO2, CDAI, symptom directed PE including body weight, vital signs, safety laboratory analyses, urine pregnancy test (for females of child-bearing potential), AEs and concomitant medications assessments will occur at each study visit.

Women of child-bearing potential will require urine pregnancy tests every 4 weeks starting from Day 1 for the entire duration of the study.

Subjects rolling over from GS-US-419-4016 will require complete perianal fistulae assessment every 12 weeks.

Urine samples will be collected at Day 1 and once every 24 weeks.

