- Subjects with positive or 2 indeterminate QuantiFERON® test result(s) who are determined as having neither latent nor active TB infection may continue participation in the study after consultation and approval from medical monitor. Any subject with active TB must be discontinued from the study. Subjects who were previously treated for TB with a complete and adequate course of therapy as per local standard of care and as verified by the investigator do not need to have yearly QuantiFERON® tests. Subjects previously treated for TB should be screened at least yearly for signs and symptoms consistent with reactivation of TB. Any subject with active TB should be discontinued from the study.
- After a confirmed laboratory change representing moderate renal impairment (estimated creatinine clearance [CrCl]  $\geq 35$  mL/min and  $< 60$  mL/min per Cockcroft-Gault [CC&G] formula) at any time during the study, the following actions should be taken by the investigator and documented:
  - Establish possible underlying condition and initiate appropriate action to resolve.
  - Retest CrCl within 8 weeks.
  - Carefully consider individual benefit/risk of continuation of filgotinib 200 mg once daily in relation to the observation.
  - If continuation of filgotinib 200 mg once daily is not considered appropriate, interrupt treatment until retest confirms CrCl  $\geq 60$  mL/min.
  - The investigator/designee should assess individual subject benefit/risk with regards to re-initiation of treatment after repeat or prolonged interruptions, or if re-initiation is not considered appropriate.
- For subjects with confirmed absolute lymphocyte count (ALC) less than 500 cells/mm^3, retest within 3 to 7 days, filgotinib should be interrupted until grade returns to  $\leq$  Grade 2 (more than 500 cells/mm^3). If ALC does not return to  $\leq$  Grade 2 within 4 weeks or returns to less than 500 cells/mm^3 following re-challenge with filgotinib, then filgotinib should be permanently discontinued and the subject managed according to local practice.

*NOTE: During the time of study drug interruption for any of the above, the subject may continue to have study visits and to take part in procedures and assessments, if deemed medically appropriate by the investigator.*

The medical monitor should consult the medical leader as needed.

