### 4.2. Inclusion Criteria

Subjects must meet *all* of the following inclusion criteria to be eligible for participation in this study.

- 1) Must have the ability to understand and sign a written ICF, which must be obtained prior to initiation of study procedures associated with this trial
- 2) Criterion modified per amendment 9
  - 2.1) Must have enrolled in a CD parent protocol, GS-US-419-4015, GS-US-419-4016, GS-US-419-3895 or any other Gilead/Galapagos-sponsored filgotinib treatment study in CD
- 3) Females of childbearing potential must have a negative pregnancy test at Day 1 and must agree to continued monthly pregnancy testing during use of filgotinib treatment
- 4) Criterion modified per amendment 9
  - 4.1) Female subjects of childbearing potential who engage in heterosexual intercourse must agree to use protocol specified method(s) of contraception for the duration described as described in [Appendix 6](#)
- 5) Willingness to refrain from live or attenuated vaccines during the study and for 12 weeks after last dose of study drug
- 6) Must have completed all required procedures or met protocol specified efficacy discontinuation criteria in a prior filgotinib treatment study for CD

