### 4.3. Exclusion Criteria

Subjects who meet any of the following exclusion criteria are not to be enrolled in this study.

- 1) Subjects who are discontinued from a parent study for reasons other than disease worsening, or lack of response or remission; eg, subjects who discontinue for safety or tolerability issues are not eligible for the present study
- 2) Known hypersensitivity to the study drug

- 3) Any chronic medical condition (including, but not limited to, cardiac or pulmonary disease, alcohol or drug abuse) that, in the opinion of the Investigator or Sponsor, would make the subject unsuitable for the study or would prevent compliance with the study protocol
- 4) Criterion modified per amendment 9
  - 4.1) Females who may wish to become pregnant and/or plan to undergo egg donation or egg harvesting for the purpose of current or future fertilization during the course of the study and for at least 30 days after the last dose of study drug
- 5) Criterion deleted per amendment 9
- 6) Criterion modified per amendment 9
  - 6.1) Females of reproductive potential who are unwilling to abide by protocol-specified contraceptive methods as defined in [Appendix 6](#)
- 7) Use of prohibited concomitant medications as outlined in Section [5.4.2](#)

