### **Day 1 LTE Procedures**

Subjects will be screened to ensure eligibility, and if confirmed, subjects will be enrolled on the same day and study drug dispensed. The following will be performed and documented at this visit:

- Obtain written informed consent
- Review inclusion/exclusion criteria and other protocol restrictions (Sections 4.2 and 4.3)
- Review medical history (ongoing AEs from prior filgotinib treatment studies should be recorded as medical history)
- Review AEs and concomitant medications
- TB Assessment QuantiFERON® (or centrally reported equivalent assay)
- Review electronic diary (e-Diary) for completion from prior filgotinib treatment study when available and remind subjects of diary instructions
- Collect the variables to calculate CDAI score (reference [Appendix 4](#))
  - Site enters patient assessments from Day 1 visit
  - CDAI score calculated centrally after all components have been captured electronically

- Baseline PRO2 (reference [Appendix 4](#)) – centrally calculated using the patient reported symptoms of stool frequency and abdominal pain captured in the electronic diary
- Symptom-directed physical examination (PE)
- Transfer a copy of the subject’s last perianal fistulae assessment into source documentation (for subjects rolling over from GS-US-419-4016 **only**)
- Obtain weight and height
- Obtain vital signs (resting blood pressure, respiratory rate, pulse, and temperature)
- Obtain blood samples (reference Study Procedures Table [[Appendix 2](#)])

— HBV Surveillance Guidelines

- Subjects with positive HBcAb and HBV DNA < LLOQ in a parent CD protocol will require ongoing HBV DNA monitoring every 3 months during this study. These subjects may also require prophylactic treatment per investigator discretion in accordance with local guidelines/standard of care.
- In Japan and where required by local guidelines, subjects with positive HBcAb and/or positive HBsAb but with HBV DNA < LLOQ in a parent CD protocol will require ongoing HBV DNA monitoring every 4 weeks for at least 12 months after starting study drug in accordance with local guidelines during this study.
- Any subject who has HBV DNA  $\geq$  LLOQ during the study will be discontinued (reference Section [3.5.2](#)).

- [REDACTED]
- [REDACTED]
- [REDACTED]

- Obtain stool samples (reference Study Procedures Table [[Appendix 2](#)])
- Obtain urine sample (reference Study Procedures Table [[Appendix 2](#)])

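### Protocol Section 1.4 says subjects with clinically significant active infections will be excluded, but no LTE eligibility criterion puts this into effect

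*Protocol*

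**What the plan says.** Protocol Section 1.4 names infection as an expected risk of JAK inhibition and reports more infection on active treatment than on placebo across the filgotinib studies. It then cites the interruption and discontinuation rules and site training as protections, and adds: "All subjects will be screened for tuberculosis (TB) and subjects with clinically significant active infections will be excluded". The malignancy statement that follows defers to the earlier trials: "subjects with recent malignancies will be excluded as outlined in the inclusion criteria in the parent study". The section goes on to conclude that the risk/benefit balance is favourable.

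The operative lists are in Sections 4.2 and 4.3. Section 4.3 opens with "Subjects who meet any of the following exclusion criteria are not to be enrolled in this study". The synopsis repeats both lists.

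Section 6.2.1 (Day 1 LTE Procedures) sets the order of events: "Subjects will be screened to ensure eligibility, and if confirmed, subjects will be enrolled on the same day and study drug dispensed". A TB assay is among that day's procedures.

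Infection rules for subjects already in the study are in Sections 3.5.1 and 3.5.2. For example, Section 3.5.1 states: "Any subject with active TB must be discontinued from the study".

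**The concern.** Investigators enrol from the eligibility lists, not from the risk/benefit discussion. If Section 1.4 promises an exclusion and the lists do not contain it, a site that follows the lists exactly can enrol and dose a subject whom the protocol elsewhere says is kept out. An ethics committee reading Section 1.4 would believe that an entry check exists.

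The subject matter makes this more than a drafting matter. Safety is the primary endpoint, and SAP Section 7.1.8 makes infections, serious infections and opportunistic infections adverse events of interest. There is also a reporting consequence: SAP Section 4.3 summarises subjects who were enrolled without meeting an eligibility criterion. A subject enrolled with an active infection breaches no listed criterion on that account, so that summary would not show the departure from Section 1.4.

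**Working it through.** There is no figure to reproduce: the protocol has no sample size calculation and the point concerns consistency of text. The check compares the Section 1.4 statement with each place that could put it into effect.

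1. **Inclusion list (Section 4.2, six items).** Consent, parent-study enrolment, pregnancy testing, contraception, live vaccines, and the manner of parent-study exit. The last reads "Must have completed all required procedures or met protocol specified efficacy discontinuation criteria in a prior filgotinib treatment study for CD". Items on active infection or a TB result: 0 of 6.

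2. **Exclusion list (Section 4.3, seven numbered items).** Parent-study discontinuation for reasons other than efficacy, hypersensitivity, chronic medical condition, pregnancy or egg-donation plans, a deleted item, contraception, and prohibited medication. Items on active infection, TB, HBV or HCV: 0 of 7. With the deleted item removed, the live criteria in both lists number 6 + (7 − 1) = 12, and none addresses active infection.

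3. **Synopsis.** The same items, ending with "Use of prohibited concomitant medications as outlined in" Section 5.4.2. Again none on infection.

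4. **Nearest general criterion.** Exclusion 3 begins "Any chronic medical condition (including, but not limited to, cardiac or pulmonary disease, alcohol or drug abuse" and depends on the opinion of the investigator or sponsor. It is limited to chronic conditions, so an acute infection falls outside its wording.

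5. **Day 1.** The TB assay is done, so the screening half of the Section 1.4 sentence is met. No criterion makes entry depend on the result, and eligibility confirmation, enrolment and dispensing share one day. The protocol gives no assay turnaround. If the result comes back later, which is an assumption, it can act only through Section 3.5.1, after dispensing.

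6. **Rules after enrolment.** Section 3.5.1 interrupts dosing for a newly positive or twice-indeterminate TB test, removes subjects with active TB, and calls for work-up and monitoring of an infection that is new during the study. Section 3.5.2 requires permanent discontinuation of drug for opportunistic infection, serious infection, complicated zoster, and active HBV or HCV. These rules govern subjects already enrolled. Section 1.4 cites the interruption and discontinuation rules separately, just before the exclusion, so the exclusion reads as an additional protection.

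7. **Parent-study criteria.** Section 1.4 attaches its parent-study reference to malignancy, not to infection. Section 6.2.1 places rollover at about parent Week 10 or 11 for non-responders and at Week 24 or Week 58 for completers; disease-worsening exits have no fixed week. Subjects from other filgotinib studies may enter up to 30 days after finishing parent end-of-study procedures. A check made at parent entry cannot show whether an infection is active on LTE Day 1.

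Result: an acute, clinically significant infection present on Day 1 triggers no listed exclusion.

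**The case against.** The strongest reply is that infection is well covered elsewhere and that Section 1.4 is background text. Much of this is fair. TB is tested on Day 1, and the rules in Sections 3.5.1 and 3.5.2 are specific and strict. Other criteria reach some cases: exclusion 1 bars anyone whose parent-study participation ended for safety reasons, exclusion 3 can reach chronic infections, and exclusion 7 with Table 5-1 bars subjects taking rifampin, rifabutin or rifapentine. The parent protocols are not available, so they may contain infection criteria or continuing infection rules. All of this narrows the gap. None of it supplies the entry criterion that Section 1.4 describes.

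Two stronger readings are tempting, and the documents support neither.

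- A reader might infer that subjects have no effective protection against infection. The Day 1 TB test and the interruption and discontinuation rules show otherwise. What is missing is the entry exclusion.
- A reader might infer that infections carried over from the parent study would be counted as LTE treatment events. Ongoing parent-study adverse events are recorded as medical history (Protocol Section 6.2.1; SAP Section 5.3). A treatment-emergent event needs onset on or after the start of LTE drug, or must lead to premature discontinuation (Protocol Section 8.6.2; SAP Section 7.1.6.1), and the summaries of adverse events of interest use treatment-emergent events. The remaining routes are narrow: a pre-existing infection that worsens (Protocol Section 7.1.1), one that leads to discontinuation of drug, or one with an incomplete onset date (SAP Section 7.1.6.2).

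**Conclusion.** Wrong as written: the protocol contradicts itself. Section 1.4 states an exclusion for clinically significant active infection, and none of the 12 live eligibility criteria implements it. The practical gap is mainly the subject with an acute infection at rollover. For serious or opportunistic infection the text is also inconsistent, since Section 3.5.2 would require drug to be stopped while no criterion specifically bars entry with that infection.

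The number of subjects affected cannot be computed from the documents. No endpoint, estimate or planned analysis changes; the consequence is for subject safety and for the accuracy of the risk/benefit statement.

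The conclusion assumes that the exclusion in Section 1.4 refers to entry into this study, as its wording suggests, and that Sections 4.2 and 4.3 are the complete operative lists, as their opening sentences indicate. It does not depend on what the parent protocols contain.

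**What to change.** Reconcile Section 1.4 with Sections 4.2 and 4.3, the synopsis lists and the Day 1 eligibility check in Section 6.2.1, so that the stated safeguard and the operative criteria agree. The text should also say whether the Day 1 TB result bears on eligibility or only on later interruption and discontinuation. Which clinical rule applies is for the sponsor to decide. If Section 1.4 is the text that changes, its risk/benefit conclusion should be re-read without that protection.

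The cost is about one line in an amendment. Day 1 already includes medical history, adverse event and medication review, a symptom-directed examination and vital signs, so no new procedure is implied. The downside is that a few rollovers might be delayed if the reconciled text operates at entry.
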